10.2.1 DISTRIBUTION OF THE PATIENTS

The number of patients in the mITT population, as well as the distribution across sites will be presented. Descriptive statistical data will be used to draw up the characteristics of subjects at the time of enrollment (demographics, baseline data).

10.2.2 HANDLING MISSING VALUES

In order to provide unbiased and informative findings, no replacement of missing values is planned for any parameters. In all applicable cases, reported analysis will mention the number of missing values for each outcome in the mITT population.

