5.8 FOLLOW-UP REQUIREMENTS

Subjects will be followed procedurally and to hospital discharge and at 1, 6 (standard of care follow-up; no specific trial visit is required), 12 months and annually through five years (total follow-up commitment).

Table 2 outlines a suggested follow-up schedule which may be altered to meet standard of care at individual sites.

If a subject undergoes conversion to open surgical repair, the subject will continue follow-up for 30-days post-conversion, at which point the subject will exit. If the subject has not been discharged from the conversion hospitalization within 30-days, the date of discharge will be the date of trial exit.

Table 2: Suggested Follow-Up Visit Schedule									
Suggested Schedule of Tests:	Screening/ Baseline	Procedure	Pre- Discharge	FUP 1 1 month 30 ± 15 days	FUP 2 6 Month 182± 30 days	FUP 3 1 Year 365± 60 days	>1 to 5 Years FUP (± 90 days window)		
Inclusion/Exclusion	X	-							
Demographics/Medical History	X								
Physical Exam [†]	X		X	X	X	X	X		
Blood Labs‡	X		X	X	X	X	X		
Contrast-enhanced CT scan	x [¥]			x [¥]	х*	x [¥]	х*		
Procedural Information		X							
Adverse Events		X	X	X	X	X	X		

[†]The physical exam includes overall health, physical assessment, and vital signs.

[‡]Blood labs typically include serum creatinine and hemoglobin, if collected

^{*} High resolution (<3mm slice spacing), contrast and non-contrast CT scan is preferred up to 3 months prior to the scheduled procedure *If the institution's standard of care for EVAR subjects involves another imaging modality e.g., duplex ultrasound, that modality may be collected alternatively.

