5 TRIAL EVALUATIONS

6.1 PRIMARY TRIAL ENDPOINTS

The primary trial endpoint is one -year survival in the absence of Aneurysm Related Complications (ARC). ARC is a composite of the most relevant EVAR related outcomes and includes:

- Peri-operative death (< 30-days)
- Aneurysm rupture
- Conversion to Open Surgical Repair (OSR)
- Endoleaks; post-operative
- Endograft migration (≥ 10mm)
- Aneurysm enlargement (≥ 5mm compared to 1-month CT)
- Endograft occlusion
- Reinterventions for device- or aneurysm-related complications

The outcomes above comprising of the ARC composite endpoint are defined in §12.1.

Imaging driven observations will be based on the one-year evaluation window (365 days \pm 60 days). If there are two diagnostic images available within the window, the convention will be to use any image with a positive finding.

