10.2 STATISTICAL METHODS

All non-imaging-driven variables in the composite endpoint will be evaluated to 1 year (day 365 post-implant), whereas imaging-driven variables will be evaluated to a 1-year window (day 365 +/- 60 days). The day of implantation will be set as day 0. Early events are defined as those occurring from the date of the procedure up to 30 calendar days post-operatively. Late events are defined as those occurring from after 30 calendar days post-operatively (from day 31 forward).

The null hypotheses for both non-inferiority and superiority will be evaluated with one-sided alpha levels of 0.05.

If the non-inferiority null hypothesis is rejected, the null hypothesis for superiority will be investigated.

Hypotheses for Non-Inferiority:

Null Hypothesis:

 $H1_0$: $\mu_A - \mu_B \le -8\%$ (AFX is inferior with respect to the primary

endpoint)

Alternative: $H1_1$: $\mu_A - \mu_B > -8\%$ (Statistical evidence of non-inferiority)

Hypotheses for Superiority:

Null Hypothesis: $H2_0: \mu_A - \mu_B \le 0$ (The two device groups have equal effect)

Alternative: $H2_1$: $\mu_A - \mu_B > 0$ (Statistical evidence of superiority)

Data for the primary endpoint will be presented as point estimates for both the treatment (AFX device) and control (proximally fixated devices), along with a 95% confidence interval for the difference. The lower bound of a one sided 95% confidence interval is used to evaluate the non-inferiority and superiority null hypotheses.

Quantitative parameters will be described using the following summary descriptive statistics: number of non-missing values, mean, standard deviation, median, first and third quartiles, and minimum and maximum values.

Qualitative parameters will be described overall using frequencies and percentages. Percentages will be calculated on the number of non-missing observations. In all cases, the number of missing values will be specified.

Kaplan-Meier estimates will be generated for the composite endpoint components across the duration of the trial.

Sample Size Determination:

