Given an alpha error rate of 0.05, a desired power of 90%, and assuming a success rate (in terms of the primary endpoint) of 86% for AFX with an 8% advantage over the control group, the sample size required to demonstrate non-inferiority is 154 subjects in total. In order to have enough power to evaluate all hypotheses the sample size for this trial was driven by the evaluation of superiority. In this case, an alpha error rate of 0.05, power of 80%, success rate of 86% for AFX, and a relative 8% advantage in AFX's favor requires 566 patients. A 7% advantage in AFX's favor requires 724 patients. An approximate dropout rate of 10%/1-year indicates 804 patients should be enrolled to provide 724 patients at 1 year. The original protocol thus called for enrollment of up to 800 subjects. The enrollment was completed at 455 subjects after an unplanned analysis supported that the superiority evaluation was futile. With a total of 455 subjects enrolled, 410 are assumed to reach the 1-year endpoint after 10% dropout. This sample size results in 99% power for the non-inferiority test under original assumptions, and thus the trial is considered adequately powered for evaluating non-inferiority. The sample size has been determined with PASS version 12.0.2.

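### Section 10.2.2 calls leaving missing values unreplaced unbiased; for a one-year composite this is not guaranteed, and no sensitivity analysis of the primary test is planned

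*Combined protocol and SAP*

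**What the plan says.** Section 10.2.2 gives the missing-data rule and its reason: "In order to provide unbiased and informative findings, no replacement of missing values is planned for any parameters". It then asks only that the number of missing values be reported for each outcome in the mITT population.

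Section 10.2 says "Percentages will be calculated on the number of non-missing observations", in a paragraph on descriptive statistics. It also says "Kaplan-Meier estimates will be generated for the composite endpoint components across the duration of the trial", which is not tied to the primary test.

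Section 6.1 defines the endpoint: "The primary trial endpoint is one -year survival in the absence of Aneurysm Related Complications (ARC"). Non-imaging components run to day 365. For imaging, section 10.2 says "imaging-driven variables will be evaluated to a 1-year window (day 365 +/- 60 days"), that is, days 305 to 425. Section 6.1 has a convention for two images in that window but none for no image.

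On the expected extent of missing data, the sample size paragraph of section 10.2 says "410 are assumed to reach the 1-year endpoint after 10% dropout". Section 5.8 adds: "Table 2 outlines a suggested follow-up schedule which may be altered to meet standard of care at individual sites".

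Section 10.1 refers to a separate SAP and section 12.1 to an Adjudication Charter. Neither is in the supplied text.

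**The concern.** A subject who has an ARC in month 2 and is lost in month 6 is a known failure. A subject without an event who is lost in month 6 has no known one-year outcome. Keeping the first and dropping the second removes potential successes selectively, so the complete-case success rate is too low even if dropout has nothing to do with prognosis. The bias largely cancels between arms when dropout is equal, and does not when it is unequal.

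After enrollment closed at 455, non-inferiority is the hypothesis the trial is said to be adequately powered for. Section 10.2.3 shows that ARC has already been analysed on site reports and will be analysed again with Core Lab data. A count of missing values would not tell a reader whether the conclusion against the -8 point margin depends on the subjects without an outcome.

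**Working it through.** **Inputs from the protocol.** 455 enrolled, 10% dropout by one year, planning rates 86% (AFX) and 78% (control, reading the 8% advantage as absolute), margin 8 points, one-sided alpha 0.05, 1:1 allocation.

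**Assumptions.** 228 AFX and 227 control subjects. Dropout is random and uniform over 365 days. The share of failures found only on the in-window image (and so lost on dropout) is 0, 50% or 80%. The other failures occur at a constant hazard, or 50% or 80% of them by day 30. The documents give none of these, nor dropout by arm.

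**The plan's own figures.** 455 × 0.90 = 409.5, so 410 reproduces, leaving 45 without an outcome. With 205 per arm, SE = √(0.86×0.14/205 + 0.78×0.22/205) = 0.0377, and power = Φ(0.16/0.0377 − 1.645) = 99.5%, against the stated 99%.

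**Bias in one arm.** Let p be true success, d dropout, and G the chance that a failure in a dropout was seen before dropout. The complete-case success rate is

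q = p(1−d) / [p(1−d) + (1−p)(1−d+dG)].

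With p = 0.78, d = 0.10, all failures clinical and 80% by day 30, G = 0.859. Then q = 0.702 / (0.702 + 0.2169) = 0.764, which is 1.6 points low. Over all timings and imaging shares the shortfall is 0.2 to 1.6 points at 78% and 0.1 to 1.1 points at 86%.

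**Type I error at the margin, true AFX 78% and control 86%.** Worked case: dropout AFX 5%, control 15%, all failures clinical, constant hazard (G = 0.521 and 0.513).
- AFX: 0.741 / (0.741 + 0.2147) = 0.7753.
- Control: 0.731 / (0.731 + 0.1298) = 0.8492.
- Difference −7.39 points instead of −8; SE 3.81 points.
- Error = Φ(0.61/3.81 − 1.645) = 6.9%.

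Simulation with the Wald bound (200,000 trials per setting; 5.0 to 5.2% with no dropout), range over event timing:

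| Dropout AFX/control | Imaging-only share 0 | 50% | 80% |
|---|---|---|---|
| 10/10 | 3.9–4.4% | 4.5–4.7% | 4.8–5.0% |
| 5/15 | 6.9–8.4% | 6.0–6.7% | 5.4–5.6% |
| 15/5 | 1.6–2.6% | 3.0–3.7% | 4.1–4.5% |

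At true rates of 70% and 78%, the ranges are 4.2–5.0% (equal), 5.4–9.9% (5/15) and 1.6–4.4% (15/5).

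**Tipping point.** One-sided 95% lower bounds in points, with 205 observed per arm and 23 AFX and 22 controls missing.
- *Planning rates 86/78:* complete case +1.8. All missing AFX fail and missing controls behave as observed: −7.1, still passes. All missing controls also succeed: −9.1, fails. It passes again at 3 of 23 AFX successes (−7.7).
- *Illustrative 82/82 (168 of 205 each; not a protocol assumption):* complete case −6.25. With 18 of 22 missing controls succeeding, 15 of 23 AFX successes give −7.71 and 14 of 23 (61%) give −8.18.

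**A separate definition point.** The section 6.1 endpoint is worded as survival, but its ARC list includes only peri-operative death. At 82/82, assume 8 AFX and 4 control deaths after day 30 without ARC, otherwise counted as successes. As failures, 160 v 164 of 205 gives −8.56; excluded, 160/197 v 164/201 gives −6.79.

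**The case against.** The strongest reply is that the bias depends on a denominator that section 10.2.2 does not spell out. If only subjects who reach one year are analysed, as the step from 455 to 410 may suggest, random dropout causes no bias. That is correct, and it is why the claim here is *not guaranteed* rather than *false*. But that denominator would discard failures already observed, which is hard to defend for a composite of complications.

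Second, the only dropout figure in the documents, 10% overall, shows no inflation. Every inflated figure above needs an assumed unequal split, and the opposite split is conservative. This stands. A reader might infer that the plan favours AFX or inflates type I error; the documents do not support that, since they give no dropout by arm.

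Third, a reader might infer that dropouts could be counted as successes. That would be a replacement of a missing value, which section 10.2.2 rules out, so it is not pursued here.

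Fourth, a reader might take the remarks on missed visits and images in section 16.1 as evidence of missing one-year data. They concern COVID-19 changes to the monitoring plan. Enrollment was completed in Q3 2017, so the day-425 windows closed around late 2018.

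Finally, an 80% imaging-only share is unsupported by the documents, and Table 2 suggests earlier scans. A high share brings the complete-case error closer to 5%, so lowering it does not weaken the point. The unseen SAP or Adjudication Charter may already hold the missing analyses.

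**Conclusion.** The point holds in a limited form. The property claimed in section 10.2.2 is not assured for this endpoint. Keeping observed failures and dropping event-free dropouts understates success by about 0.1 to 1.6 points at 10% random dropout. With equal dropout the non-inferiority test is nominal or conservative. With an assumed 5% AFX and 15% control split, type I error is about 5.4 to 8.4% at true 78/86, and up to 9.9% at 70/78. At the planning rates the conclusion is robust to all but a near-worst case; with observed rates near equality it would be more fragile.

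The gap is that the supplied text offers no analysis to show which situation applies. Dropout splits, imaging shares, event timing and death counts are all assumptions, and the direction of any actual effect is unknown. This is an improvement worth making, not a defect that invalidates the primary test.

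**What to change.** 1. Delete or qualify the word unbiased in section 10.2.2.
2. State that any mITT subject with an observed ARC event is a failure, even without one-year data. This is the denominator that understates success, so it should be paired with item 4(b).
3. Keep the planned primary test.
4. Add two analyses on all mITT subjects, labelled as sensitivity analyses because ARC has already been analysed: (a) an arm-specific tipping-point grid against the −8 point margin, covering dropouts and subjects without an image in days 305 to 425; (b) the difference in one-year Kaplan-Meier ARC-free survival with a one-sided 95% lower bound, censoring event-free subjects without one-year data at last contact. State how in-window images after day 365 are dated. Kaplan-Meier assumes non-informative censoring, which is why (a) is also needed.
5. Report evaluable counts by arm.
6. Separately, reconcile survival in the section 6.1 endpoint with an ARC list that names only peri-operative death.

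If the separate SAP or the Adjudication Charter already contains these analyses, cross-refer to it. The cost is a few sentences and modest programming, with no new visits or data. The non-inferiority conclusion may look less robust as a result.

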10.2.3 DATA ANALYSIS

In the original analyses, the ARC endpoint has been evaluated by site reported events only. Now that Corelab data is available, it will be considered during the future evaluations of the data.

In future analyses, the data presented will utilize CoreLab findings in addition to site-reported findings. The analyses will defer to CoreLab results when the site and CoreLab disagree. In the absence of CoreLab-reviewed data, events will be assessed by the site. In addition to this, the clinical data and evaluation of the patients will be considered when reviewing data, and the clinical history of the patient as well as the review of the independent adjudicator may overrule site and Corelab findings.

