Secondary Endpoints	 MAEs at 30-Days, 12 Months and Annually ARC Post 12 Months up to Five Years Aneurysm Related Mortality Endoleaks Classified by Type AAA Related Secondary Procedures up to Five Years Device integrity Any adjunctive procedures necessitated during the implant procedure 					
Additional Evaluations	 Total Endovascular time; from catheter introduction to catheter removal Anaesthesia Time Fluoroscopy Time Contrast Volume used Total Procedure Time; from cut-down to closure Time in ICU Total Radiation Exposure Additional Imaging 					

Statistical Considerations

The primary endpoint will be evaluated in both the AFX and proximally fixated device groups. The relative performance of the two groups will be evaluated through one-sided tests for non-inferiority and superiority. Combining the superiority and non-inferiority trials into a single closed testing procedure allows for maintenance of a controlled Type 1 error rate. An 8% margin will be used for the non-inferiority test. If the non-inferiority null hypothesis is rejected, the null hypothesis for superiority will be investigated.

Hypotheses for Non-Inferiority:

Null Hypothesis: $H1_0$: $\mu_A - \mu_B \le -8\%$ (AFX is inferior with respect to the

primary endpoint)

Alternative: $H1_1: \mu_A - \mu_B > -8\%$ (Statistical evidence of non-

inferiority)

Hypotheses for Superiority:

Null Hypothesis: $H2_0$: $\mu_A - \mu_B \le 0$ (The two device groups have equal effect)

Alternative: $H2_1$: $\mu_A - \mu_B > 0$ (Statistical evidence of superiority)

The original trial size was selected to provide 80% power for the superiority test. The original sample size required, for non-inferiority testing, is relatively smaller; thus, the power of the non-inferiority test approaches 100% with the revised sample size.

Suggested Schedule of Tests

Patient eligibility will be assessed by the Investigator per institutional standard of care pre-procedural imaging. Blood work and physical exam will also be collected as per routine schedule at each institution.

Following Institutional Review board approval and patient written informed consent, the patient will be screened for eligibility. Subjects will be followed procedurally and to hospital discharge and per institutional standard of care thereafter through to 5 years (total follow-up commitment).

Table 1 outlines a typical site follow-up schedule which will be altered to meet standard of care at individual sites.

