13.3 INDEPENDENT EVENT REVIEWER RESPONSIBILITIES

An independent physician(s) will adjudicate all MAEs, ADEs, SADEs and UADEs reported by the sites within this trial. The independent physician will complete the eCRF data capture form for all the adjudicated events.

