13.4 INDEPENDENT CORE LAB RESPONSIBILITIES

All images obtained in this trial will be assessed by an external, independent Core Lab and measurements of the assessment will be recorded in the eCRF, to ensure uniform and unbiased image assessment throughout the trial.

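### Section 10.2.3, written after earlier analyses of the endpoint, allows discretionary overrides of site and core-lab findings on the primary endpoint, with no stated criteria, direction, timing or masking to arm

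*Combined protocol and SAP*

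**What the plan says.** The primary endpoint is one-year survival free of aneurysm-related complications (ARC), a composite of clinical and imaging components (section 6.1).

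Section 10.2.3 describes how its data source changed: "In the original analyses, the ARC endpoint has been evaluated by site reported events only". From then on core-lab findings are used as well. The core lab prevails where it disagrees with the site, and the site's assessment stands where there is no core-lab read. A last step sits above both: "the clinical history of the patient as well as the review of the independent adjudicator may overrule site and Corelab findings".

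Other places bear on this step:

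- Section 10.2, sample size: "The enrollment was completed at 455 subjects after an unplanned analysis supported that the superiority evaluation was futile".
- Section 13.3: the independent physician "will adjudicate all MAEs, ADEs, SADEs and UADEs reported by the sites within this trial". The synopsis says the same. Section 11 lists ADEs, MAEs and SADEs.
- Section 13.4: the core lab reads all images "to ensure uniform and unbiased image assessment throughout the trial".
- Section 6.1: where two images fall in the one-year window, a positive one is used.
- Section 12.1: an Adjudication Charter is cited for elaboration of the ARC definitions.
- Section 10.1: the only blinding mentioned is of sites and investigators to block size.

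**The concern.** The override decides who counts as a failure in the primary non-inferiority test, and four things about it are left open.

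1. **Who and when.** The adjudicator is a named role, but clinical history is not a person. Nobody is identified as applying that route. The step is permissive, and no circumstance is given in which it should or should not be used.
2. **Safeguards.** No direction, log, deadline or masking to treatment arm is stated.
3. **Timing.** The wording itself looks back on completed ARC analyses, and a futility judgement on superiority requires a comparison of the arms. Enrollment completion is given as Q3 2017 and Revision 02 is dated 29 August 2021, about four years later. A discretionary rule for the primary endpoint written at that stage is hard to defend, even if it is applied in good faith.
4. **Fit with the rest of the protocol.** The adjudicator's intake is defined by site-reported event classes. The MAE list in section 12.3 does not contain rupture, conversion, endoleak, migration, enlargement, limb occlusion or reintervention as such. These reach the adjudicator only if the site reports them as a device effect or they coincide with an MAE. A finding made only by the core lab has no stated route there, yet section 10.2.3 lets the adjudicator overrule it. Nor is the any-positive-image convention ranked against the override.

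At stake is whether a non-inferiority statement can be traced to a rule fixed independently of the results.

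**Working it through.** **Inputs from the plan.** "The null hypotheses for both non-inferiority and superiority will be evaluated with one-sided alpha levels of 0.05" (section 10.2). "An 8% margin will be used for the non-inferiority test" (synopsis). The planning assumption is a "success rate (in terms of the primary endpoint) of 86% for AFX with an 8% advantage over the control group" (section 10.2). Of 455 enrolled, 410 are assumed evaluable; at 1:1 that is 205 per arm.

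**Formula.** Unpooled normal approximation, with d the expected observed difference in success (AFX minus control):

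P(claim non-inferiority) = Φ((0.08 + d)/SE − 1.645), SE = √[(p_A(1−p_A) + p_B(1−p_B))/205]

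**The plan's own figure.** With 86% against 78%, d = +0.08 and SE = 0.0377. Then 0.16/0.0377 = 4.24, and Φ(4.24 − 1.645) = 99.5%, which agrees with the stated 99%. Reading the 8% as absolute also reproduces the stated 566 for superiority.

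**How many patients decide the test.** One patient is 1/205 = 0.49 points of an arm's rate. If both observed rates are near 78%, SE = 0.0409 and the one-sided half-width is 1.645 × 4.09 = 6.7 points. The test then passes only if the observed AFX deficit is at most 8 − 6.7 = 1.3 points, or 2 patients.

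**False non-inferiority at a true 8-point deficit.** Two settings were used: failure of 22% AFX vs 14% control, and 30% vs 22%. With no override the result is 5% in both. The documents give no override rate, so every count below is an assumption.

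| Assumed reclassification | 22% vs 14% | 30% vs 22% |
|---|---|---|
| 2 true AFX failures overruled | 8.3% | 7.8% |
| 5 true AFX failures overruled | 16.3% | 14.2% |
| 10% of true failures overruled in both arms | 7.7% | 7.3% |
| 20% of true failures overruled in both arms | 11.9% | 10.7% |
| 5 AFX failures added | 1.1% | 1.4% |

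Worked case, 5 overruled at 22% vs 14%: AFX failure becomes 22 − 5 × 0.488 = 19.56%, so d = −5.56 points and SE = 3.68 points. Then (8 − 5.56)/3.68 = 0.663, and Φ(0.663 − 1.645) = 16.3%.

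Worked case, 10% overruled in both arms at 30% vs 22%: the rates become 27.0% and 19.8%, so d = −7.2 points and SE = 4.17 points. Then 0.8/4.17 = 0.192, and Φ(0.192 − 1.645) = 7.3%.

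**The opposite case.** If the recorded failures include false positives, the override can help. At true failure of 30% vs 22%, a false-positive rate of 5% or 10% in both arms raises false non-inferiority to 6.0% or 7.0%. Removing exactly those findings restores 5%.

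**The case against.** The best defence is that clinical adjudication above image reads is legitimate. Death, conversion and reintervention cannot be settled from images alone, and both the adjudicator and the core lab are described as independent. Criteria and masking may be in the Adjudication Charter, which was not available for this review, or in the SAP cited in section 10.1, of which the combined document contains no separate text. The scenarios above are hypothetical. All of this stands. It limits what can be claimed, but section 10.2.3 refers to neither document for its override, and section 12.1 cites the Charter only for definitions.

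A reader might infer more than the documents support:

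- **That review was unblinded.** The documents are silent on masking to arm, and silence does not show its absence.
- **That overrides can only remove failures.** No direction is stated. Core-lab positives that a site missed are added, because all images go to the core lab and it prevails over the site. The any-positive-image convention also favours counting a failure.
- **That overrides in general dilute a difference.** This happens only when true failures are overruled; correcting false positives works the other way.
- **That the endpoint is tested twice at full alpha.** Section 10.2.3 reads as replacing the data source, not as offering two tests of which either may succeed.
- **That the core lab's purpose is defeated.** Its stated purpose is uniform image assessment, which a well-defined clinical review need not undo.

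**Conclusion.** The concern holds as a defect in how the primary endpoint is determined, not as evidence of bias. The rule is discretionary, one of its two routes has no decision-maker, its safeguards are unstated, and it postdates analyses of the same endpoint. It also does not fit the adjudicator's intake or the imaging convention.

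The direction of any effect is unknown. The sensitivity is clear: overruling 2 true AFX failures moves a nominal 5% error to about 8%, 5 moves it to 14–16%, and a 10% loss of true failures in both arms moves it to 7–8%. Adding 5 AFX failures moves it to 1.1–1.4%. These figures rest on 205 evaluable per arm, a true 8-point deficit, the normal approximation and assumed override counts. The change should be made before any further analysis of the primary endpoint.

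**What to change.** In section 10.2.3:

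1. Fix one order: core lab for imaging components, independent adjudicator for clinical components, and site only where neither exists. Delete clinical history as a separate override; it can be part of what the adjudicator reviews.
2. Allow overrides only by the independent adjudicator, masked to arm as far as possible, under written criteria that apply in both directions. Log each override with its reason and finish them all before the new analysis is run. If the Charter already contains such rules, cite them here.
3. Reconcile sections 6.1, 10.2.3, 11 and 13.3 on which events and core-lab findings reach the adjudicator, and rank the any-positive-image convention against the override.
4. Tabulate overrides by arm and direction. Report the final-rule result beside two sensitivity analyses, one with no overrides and one with the original site-reported rule, and state whether the conclusion against −8% changes.

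Do not require all three versions to pass. That would give a veto to the site-only source being replaced. With no true difference and assumed correlations of 0.7–0.95 between versions, the chance of success would fall from 75% to 60–69% at 86% success in both arms, or from 62% to 44–55% at 78%.

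The cost is protocol and SAP wording, minor charter work and two extra runs of the same analysis. No new patients, visits or imaging are needed. The downside is a weaker non-inferiority statement if the versions disagree.
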